All AEs observed during the study will be reported on the CRF. All AEs, regardless of relationship to study drug or procedure, should be collected beginning from the time the subject signs the study ICF through the last visit. Subjects who fail screening primarily due to AE(s) must have the AE(s) leading to screen failure reported on the Screening Disposition CRF.

Abnormal laboratory values should not be listed as separate AEs if they are considered to be part of the clinical syndrome that is being reported as an AE. It is the responsibility of the investigator to review all laboratory findings in all subjects and determine if they constitute an AE. Medical and scientific judgment should be exercised in deciding whether an isolated laboratory abnormality should be classified as an AE. Any laboratory abnormality considered to constitute an AE should be reported on the Adverse Event CRF.

Abnormal ECG (QTc) results, if not otherwise considered part of a clinical symptom that is being reported as an AE, should be considered an AE if the QTc interval is more than 480 ms and there is an increase of more than 60 ms from baseline. Any ECG abnormality that the investigator considers as an AE should be reported as such.

Progression of malignant disease should not be recorded as an AE in studies where it is included as an endpoint for underlying disease. If the progression leads to an untoward medical occurrence (increased pain, pleural effusion, etc), then this medical occurrence should be the AE. Disease progression is a study endpoint and is to be captured in the case report form per the guidelines for reporting disease progression.

All AEs must be followed for 28 days after the subject's last dose, or until resolution, whichever comes first. Subjects with onset of an AE or deterioration of a preexisting AE will be followed until resolution to baseline, start of a new anticancer treatment, or death.

**Every effort must be made by the investigator to categorize each AE according to its severity and its relationship to the study treatment.**

Adverse events will be graded on a 5-point scale according to CTCAE v4.03 ([Appendix 6](#)). Investigators will report CTCAE grades for all AEs (for both increasing and decreasing severity). For Grade 2 AEs that lead to changes in study drug administration (dose held, dose reduced, or dosing discontinuation), the investigator will be required to confirm in the CRF that the AE is considered intolerable.

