## Appendix 6 Common Terminology Criteria for Adverse Events (v4.03)

The National Cancer Institute’s Common Terminology Criteria for Adverse Events (CTCAE) v4.0 [published 28 May 2009 (v4.03: 14 June 2010)] provides descriptive terminology to be used for adverse event reporting in clinical trials. A brief definition is provided to clarify the meaning of each AE term. To increase the accuracy of AE reporting, all adverse event terms in CTCAE version 4.0 have been correlated with single-concept, Medical Dictionary for Regulatory Activities (MedDRA®) terms.

CTCAE v4.0 grading refers to the severity of the AE. CTCAE grades 1 through 5, with unique clinical descriptions of severity for each AE, are based on this general guideline:

Grade	CTCAE Status
1	Mild: asymptomatic or mild symptoms; clinical or diagnostic observations only; intervention not indicated.
2	Moderate: minimal, local, or noninvasive intervention indicated; limiting age-appropriate instrumental activities of daily living (ADL). a
3	Severe or medically significant but not immediately life-threatening: hospitalization or prolongation of hospitalization indicated; disabling, limiting self-care ADL. b
4	Life-threatening consequences: urgent intervention indicated.
5	Death related to adverse event.

CTCAE = Common Terminology Criteria for Adverse Events.

a: Instrumental ADL refers to preparing meals, shopping for groceries or clothes, using the telephone, managing money, etc.

b: Self-care ADL refers to bathing, dressing and undressing, feeding self, using the toilet, taking medications, and not bedridden.

Adapted from the Cancer Therapy Evaluation Program, NCI. CTCAE v4.0. Available from: <http://evs.nci.nih.gov/ftp1/CTCAE/About.html> (Accessed 25 Jun 2015).

For further details regarding MedDRA, refer to the MedDRA website at: <http://www.meddra.org/>. CTCAE v4.03 is available online at: <http://evs.nci.nih.gov/ftp1/CTCAE/About.html> (Accessed 25 Jun 2015).

---

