5.1.1 Primary Endpoints

- ORR_{24wk} as assessed by the investigator using RECIST 1.1. ORR_{24wk} is defined as the proportion of subjects with best overall response (BOR) of complete response (CR) or partial response (PR) at the Week 24 time point or earlier. The BOR for each subject will be determined based on RECIST 1.1 without a requirement for response confirmation.
- Rate of TEAEs with CTCAE grades of 3 or higher within 24 weeks after randomization (as of the Week 24 time point).

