5.6.2 Adverse Events

The AE verbatim descriptions (investigator terms from the CRF) will be classified into standardized medical terminology using the MedDRA. Adverse events will be coded to MedDRA (version 23.0) lower level term (LLT) closest to the verbatim term. The linked

MedDRA PT and primary SOC will also be captured in the database. The CTCAE grading (version 4.03) will be included in the database.

A TEAE is defined as an AE that emerged during treatment (from time of first dose up to 28 days following the last dose of study drug), having been absent pretreatment (Baseline) or

- Reemerged during treatment, having been present pretreatment (Baseline) but stopped before treatment, or
- Worsened in severity during treatment relative to the pretreatment state, when the AE was continuous

Only TEAEs will be summarized. A subject will be counted only once within each category (i.e., SOC, PT, worst grade, or other specific category to be summarized in table) even if the subject experienced more than 1 TEAE within the category. All AEs, treatment-emergent or otherwise, will be presented in subject data listings.

For the analysis of the primary safety endpoint of rate of TEAEs with CTCAE Grade ≥ 3 within 24 weeks after randomization (as of the Week 24 time point), the number (percentage) of subjects with TEAEs of CTCAE Grade ≥ 3 as of Week 24 will be reported; the difference in frequency between the treatments (18 mg minus 24 mg) will be presented with 95% CI, using asymptotic normal approximation. In addition, the number (percentage) of subjects with TEAEs with CTCAE Grade ≥ 3 as of the Week 24 will be summarized by SOC and PT.

The incidence of TEAEs will be reported as the number (percentage) of subjects with TEAEs by SOC, PT and worst CTCAE grade. The number (percentage) of subjects with TEAEs will also be summarized by PT and worst CTCAE grade.

The number (percentage) of subjects with treatment-related TEAEs, TEAEs leading to treatment discontinuation, TEAEs leading to dose reduction/interruption, will be summarized by SOC, PT and worst CTCAE grade. All SAEs, treatment-related SAEs, fatal TEAEs, and nonfatal SAEs will be summarized by SOC and PT. Treatment-related TEAEs include those events considered by the investigator to be related to study treatment or TEAEs with a missing causality on the CRF.

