In addition, summaries of clinically significant TEAEs (CSEs) (i.e., subject incidence, time to first onset of Grade 3 or 4) will be provided. [Appendix 13.2](#) includes the list of CSEs. These CSEs include those AEs known to be of concern with lenvatinib or of VEGF-targeted agents in general.

TEAEs, SAEs, treatment-related TEAEs, treatment-related SAEs, CSEs will also be summarized by PT in decreasing frequency.

The number (percentage) of subjects with all deaths and deaths on treatment or within 30 days of last lenvatinib dose will be summarized.

Subject data listings for (1) all AEs, (2) AEs of CTCAE Grade 2 (intolerable) or above, (3) serious adverse events, (4) fatal AEs, (5) all deaths, (6) AEs leading to treatment discontinuation, and (7) AEs leading to dose reduction or interruption will be provided.

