13 APPENDICES

13.1 Clinically Significant TEAEs

The following are the Clinically Significant AE groups considered in analyses:

1. Arterial Thromboembolic Events
2. Cardiac Dysfunction
3. Fistula Formation
4. GI Perforation
5. Hemorrhage
6. Hepatotoxicity
7. Hypertension
8. Hypocalcemia
9. Hypothyroidism
10. Palmar Plantar Erythrodysesthesia Syndrome
11. Posterior Reversible Encephalopathy Syndrome
12. Proteinuria
13. QT Prolongation
14. Renal Events

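### The time-to-first-onset summary for clinically significant adverse events stops at Grade 4, so an event whose first severe grade is fatal gives no onset time in that one table

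*SAP*

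**What the plan says.** SAP section 5.6.2 (Adverse Events) introduces summaries of CSEs and describes them in a parenthesis as "subject incidence, time to first onset of Grade 3 or 4". The 14 event groups concerned are listed in SAP Appendix 13.1. They include "Arterial Thromboembolic Events", cardiac dysfunction, gastrointestinal perforation and hemorrhage.

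On grading, Protocol section 9.5.1.4.1 says: "Adverse events will be graded on a 5-point scale according to CTCAE v4.03". Protocol Appendix 6 gives the top grade its own definition, "Death related to adverse event".

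Elsewhere the SAP uses an open-ended threshold. SAP section 5.1.1 defines the primary safety endpoint as "Rate of TEAEs with CTCAE grades of 3 or higher within 24 weeks after randomization", and section 5.6.2 carries that into the analysis: "the number (percentage) of subjects with TEAEs of CTCAE Grade ≥ 3 as of Week 24 will be reported". Section 5.6.2 also provides for deaths separately: "All SAEs, treatment-related SAEs, fatal TEAEs, and nonfatal SAEs will be summarized by SOC and PT".

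**The concern.** The trial asks whether the lower starting dose has a better safety profile, and the onset summary is the planned output that shows when severe toxicity of special interest begins in each arm. Several of the listed groups are ones where the first severe presentation could plausibly be a fatal one. A definition that ends at Grade 4 leaves that presentation without an onset time. The SAP gives no reason for using a narrower range here than for the primary safety endpoint, and SAP section 7 (Changes in the Planned Analyses) does not list it as a deliberate choice. At stake is the completeness of one descriptive table, not a test or a decision rule.

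**Working it through.** No arithmetic applies. The question is what counts as an event, so the check sets the passages side by side and follows each type of subject through the rule.

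**Inputs**

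| Item | Where | What it gives |
|---|---|---|
| Event for CSE onset | SAP 5.6.2 | Grade 3 or Grade 4; Grade 5 not named |
| Grading scale | Protocol 9.5.1.4.1 | Five grades |
| Grade 5 | Protocol Appendix 6 | Fatal, separate from Grade 4 |
| Primary safety threshold | SAP 5.1.1 and 5.6.2 | Grade 3 and above, so Grade 5 counts |
| Recording of grades | Protocol 9.5.1.4.1 | "Investigators will report CTCAE grades for all AEs (for both increasing and decreasing severity" |
| Kaplan-Meier method for safety times | SAP 5.6.1 | Stated only for first dose reduction and for discontinuation due to an adverse event |
| Censoring rules | SAP 8.4 | PFS, PFS2 and OS only |

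**Step 1: is Grade 5 brought back in anywhere?** No. Neither the rest of SAP 5.6 nor SAP 8.4 adds Grade 5 to the onset definition or says how a subject with a fatal CSE is handled in that summary.

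**Step 2: apply the rule as written.**

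- *Case A.* The CSE has no recorded Grade 3 or 4 phase, and its first grade of 3 or more is Grade 5. There is no qualifying onset. If onset times are described only among subjects with an event, the subject is left out. If Kaplan-Meier is used, the subject is censored. The SAP does not say which.
- *Case B.* The CSE is recorded at Grade 3 or 4 and later becomes fatal. Onset is counted at the Grade 3 or 4 date. Because all grade changes are to be reported, this date should be available.
- *Case C.* The subject had an earlier Grade 3 or 4 event in the same group and later a separate fatal one. First onset is already fixed by the earlier event.

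Only Case A is affected.

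**Step 3: apply the amended rule, Grade 3 or higher.** Case A gains an onset at the Grade 5 date. Cases B and C do not change.

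**Step 4: where else does a Case A subject appear?**

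- CSE subject incidence, which has no grade limit in SAP 5.6.2.
- The treatment-emergent event tables by worst CTCAE grade.
- The fatal-event summary by system organ class and preferred term, the death counts, and the listings of fatal events and of all deaths.
- The primary safety endpoint, if the event falls within 24 weeks of randomization.

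None of these is specified to give a time to onset, so they keep the event visible but do not supply the missing time.

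**The case against.** The strongest reply is that nothing of substance is lost. Reporting the onset of nonfatal severe toxicity next to a separate table of fatal events is a coherent choice, and the same SAP uses Grade 3 or 4 for laboratory results in section 5.6.3. Fatal CSEs stay visible in all the outputs listed in Step 4. Most fatal events may pass through a recorded Grade 3 or 4 phase and so be counted already. The table shells are a separate document (SAP section 11) and may define the event more fully.

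Most of this stands and sets the size of the point. It does not remove it: the SAP never says that the onset summary is meant to be nonfatal only, and the laboratory wording does not carry over naturally to clinical event groups that can be fatal.

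Three stronger readings are tempting and are not supported.

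- *A reader might infer that subjects with a fatal CSE are treated as never having had a severe event.* The SAP contains no such rule. The consequence is confined to the onset summary, and even there the handling (omitted or censored) is unstated.
- *A reader might infer that the Grade 4 limit is what stops this table from reconciling with the primary safety endpoint.* The two would not reconcile in any case. The primary endpoint is a proportion of subjects, covers all treatment-emergent events and ends 24 weeks after randomization. The CSE summary is a time to onset, covers 14 selected groups, has no stated 24-week limit, and falls under the SAP 5.6 convention that Study Day 1 is the first dose.
- *A reader might size the problem as one subject's share of the 76 in an arm, or of an assumed number of severe events.* That would measure a change in incidence, which is not affected. It says nothing about a time-to-onset summary.

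**Conclusion.** The point holds in a narrow form. On the wording of SAP 5.6.2, a CSE whose first recorded grade of 3 or more is Grade 5 contributes no onset time. This rests on reading the grade range literally and on the shells not already saying otherwise, which cannot be checked from the documents. The number of such subjects cannot be derived and may be zero. Only this descriptive summary is touched; neither primary endpoint, nor the alpha, power or sample size, is affected. It is a free improvement: worth making because it is simple and removes an unexplained gap, not because any conclusion of the trial turns on it.

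**What to change.** In SAP section 5.6.2, change the onset definition for CSEs from Grade 3 or 4 to **Grade 3 or higher (including Grade 5)**, and align the table shells if they carry the same wording.

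Preferably, state in the same sentence whether onset is summarized among subjects with an event or by Kaplan-Meier, and in the latter case how subjects without an event, including those who die of other causes, are censored. The wording change alone does not settle that.

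While the passage is open, correct its cross-reference: it points to Appendix 13.2 for the CSE list, but the list is in Appendix 13.1 and 13.2 is the tumor staging system.

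The cost is a few words of SAP text and, if needed, a shell label. Onset dates already counted stay as they are; only events that are fatal when first severe are added. No data collection changes.

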5.6.3 Laboratory Values

Clinical laboratory test parameters, per category, are listed in Table 2. The results will be standardized using System International (SI) units and categorized according to CTCAE grade (v4.03) (see protocol Appendix 13.8).

Table 2 Clinical Laboratory Tests

Category	Parameters
Hematology	Hematocrit, hemoglobin, MCH, MCHC, MCV, platelets, RBC count, and WBC count with differential (bands ^a , basophils, eosinophils, lymphocytes, monocytes, neutrophils), INR ^b
Chemistry	Bicarbonate ^a , chloride, potassium, sodium, BUN or urea, creatinine, glucose, magnesium, phosphorus, calcium, albumin, total protein, alkaline phosphatase, ALT, AST, conjugated (direct) bilirubin, total bilirubin, TSH, Amylase ^e , lipase, CPK ^c , LDH ^f , Total cholesterol, triglycerides, free T4 levels ^f
Urine Dipstick Testing^d	glucose, hemoglobin (or blood), ketones, pH, protein ^c , specific gravity

ALT = alanine aminotransferase, AST = aspartate aminotransferase, BUN = blood urea nitrogen, CPK = creatine phosphokinase, β -hCG = beta-human chorionic gonadotropin, INR = International Normalized Ratio, LDH = lactate dehydrogenase, MCH = mean corpuscular hemoglobin, MCHC = mean corpuscular hemoglobin concentration, MCV = mean corpuscular volume, RBC = red blood cells, T4 = thyroxine, TSH = thyroid stimulating hormone, UPCR = urine protein-to-creatinine ratio, WBC = white blood cells.

a: Optional if results cannot be obtained from the local laboratory.

b: INR should only be performed as part of the screening assessment and when clinically indicated.

c: Amylase isoenzymes (pancreatic and salivary type) and CPK isoenzymes (CK-MM and CK-MB) should be evaluated if amylase or CPK is greater than $3 \times$ the upper limit of normal.

d: If urine dipstick testing suggests a urinary tract infection, or if clinically indicated, a urine microscopy, culture, and sensitivity should be performed at the institution's laboratory.

e: If urine protein is $\geq 2+$, then a 24-hour urine collection or an immediate spot UPCR test should be done to quantify the 24-hour urine protein excretion.

f: For screening only.

Each parameter will be summarized or plotted by visit (with at least 10% of subjects) for actual value observed and change from Baseline. For thyroid stimulating hormone (TSH), the lowest postbaseline values will be summarized per category (≤ 0.5 ; $>0.5-2.0$; $>2.0-5.5$; >5.5 mIU/L).

Shift tables from Baseline to worst postbaseline CTCAE grade will be provided for hematology, chemistry, dipstick, and 24-hour urine collection. Grade 3 or 4 treatment-emergent laboratory results for hematology and chemistry will also be summarized.

5.6.4 Vital Signs

Each parameter of vital signs assessments (diastolic and systolic BP, pulse rate, respiratory rate, temperature) and body weight will be summarized/plotted by visit (only those having results for $\geq 10\%$ of subjects) for the actual value observed and its change from Baseline. Hypertension, based on diastolic and systolic BP measurements, will also be summarized as shift from Baseline to worst postbaseline grade (see Table 3 for CTCAE grading).

Table 3 Blood Pressure Grading per CTCAE Version 4.03

Grade	Blood Pressure (mm Hg)	
	Systolic	Diastolic
1 (Prehypertension)	120 – 139	80 – 89
2 (Stage 1 Hypertension)	140 - 159	90 – 99
3 (Stage 2 Hypertension)	≥ 160	≥ 100

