**Table 3 Study Treatments**

Total Dose (QD)	Capsule Allocation			
	10 mg Lenvatinib	10 mg Placebo	4 mg Lenvatinib	4 mg Placebo
24 mg	2	0	1	1
20 mg	2	0	0	2
18 mg	1	1	2	0
14 mg	1	1	1	1
10 mg	1	1	0	2
8 mg	0	2	2	0
4 mg	0	2	1	1

QD = once daily.

Each carton containing 2 blister cards will contain 16 doses (2 weeks plus 2 days allowing for a 2-day visit window). The investigator will have discretion to dispense up to 2 cartons simultaneously to a subject if it is appropriate for the subject to not return to clinic for 28 days.

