The following guidelines should be followed for the management of systolic BP  $\geq$ 140 mmHg up to  $<$ 160 mmHg or diastolic BP  $\geq$ 90 mmHg up to  $<$ 100 mmHg confirmed on repeat assessment after at least 30 minutes:

- Continue lenvatinib and initiate antihypertensive therapy, if not already receiving.
- Continue lenvatinib and increase the dose of the current antihypertensive therapy or initiate additional antihypertensive therapy.

The following guidelines should be followed for the management of systolic BP  $\geq$ 160 mmHg or diastolic BP  $\geq$ 100 mmHg confirmed on repeat assessment after at least 30 minutes:

- Continue study drug and institute antihypertensive therapy for subjects not already receiving this.
- For those subjects already on antihypertensive medication, the dose of the current agent may be increased, if appropriate, or one or more agents of a different class of antihypertensive should be added.
- If systolic BP  $\geq$ 160 mmHg or diastolic BP  $\geq$ 100 mmHg persists despite maximal antihypertensive therapy, then study drug administration should be interrupted and restarted at one dose level reduction only when systolic BP  $\leq$ 150 mmHg and diastolic BP  $\leq$ 95 mmHg and the subject has been on a stable dose of antihypertensive medication for at least 48 hours.
  - If systolic BP  $\geq$ 160 mmHg or diastolic BP  $\geq$ 100 mmHg recurs on the first dose reduction despite optimal management of hypertension with antihypertensive medications (either by dose increase or the addition of a different class of antihypertensive), then study drug administration should be interrupted and restarted at an additional dose reduction only when systolic BP  $\leq$ 150 mmHg and diastolic BP  $\leq$ 95 mmHg and the subject has been on a stable dose of antihypertensive medication for at least 48 hours.
  - If systolic BP  $\geq$ 160 mmHg or diastolic BP  $\geq$ 100 mmHg recurs on the second dose reduction despite optimal management of hypertension with antihypertensive medications (either by dose increase or the addition of a different class of antihypertensive), then study drug administration should be interrupted and restarted

at a third dose reduction dose only when systolic BP  $\leq 150$  mmHg and diastolic BP  $\leq 95$  mmHg and the subject has been on a stable dose of antihypertensive medication for at least 48 hours.

- Additional dose reduction should be discussed with the sponsor.

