- h. Subjects with systolic BP  $\geq 160$  mmHg or diastolic BP  $\geq 100$  mmHg must have their BP monitored on Day 15 or more frequently as clinically indicated) until systolic BP has been  $\leq 150$  mmHg and diastolic BP has been  $\leq 95$  mmHg for 2 consecutive treatment cycles. If a new event of systolic BP  $\geq 160$  mmHg or diastolic BP  $\geq 100$  mmHg occurs, the subject must resume the Day 15 evaluation until systolic BP has been  $\leq 150$  mmHg and diastolic BP has been  $\leq 95$  mmHg for 2 consecutive treatment cycles.
- i. A comprehensive physical examination (including a neurological examination) will be performed at the Screening or Baseline Visits, on Cycle 1/Day 15, on Day 1 of each subsequent cycle, and at the Off-treatment assessment. A symptom-directed physical examination will be performed on C1D1 and at any time during the study, as clinically indicated.
- j. Required if screening physical examination was performed >7 days prior to C1D1.
- k. Single 12-lead ECG. Subjects must be in the recumbent position for a period of 5 minutes prior to obtaining ECG.
- l. An echocardiogram or MUGA scan to assess left ventricular ejection fraction (LVEF) will be performed at Screening and as clinically indicated.

- m. A serum or urine pregnancy test will be performed at the Screening Visit, at the Baseline Visit (or within 72 hours prior to the first dose of study drug), at Day 1 of every cycle (starting with Cycle 2), and at the off-treatment assessment in women of childbearing potential (ie, premenopausal and perimenopausal women who have been amenorrheic for less than 12 months).
- n. The screening electrolyte results must be reviewed and confirmed to be within the normal (or reference) range prior to randomization of the subject. Clinical chemistry and hematology results must be reviewed prior to administration of study drug on C1D1 and within 48 hours after dispensing study drug for all subsequent cycles. Scheduled assessments may be performed within 72 hours prior to the visit. If there is Grade  $\geq 3$  hematologic or clinical chemistry toxicity, repeat the specific laboratory test and AE assessment at least every 3 days (until improvement to Grade  $< 3$ ).  
On Cycle 1 Day 15 and Cycle 2 Day 15, only liver function tests (albumin, total protein, alkaline phosphatase, ALT, AST, conjugated (direct) bilirubin, total bilirubin) will be performed.

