- o. For subjects with a history of proteinuria  $> 2+$ , urine dipstick testing should be performed every 2 weeks. If proteinuria  $\geq 2+$  is detected on urine dipstick testing, study drug will be continued and a 24-hour urine collection for total protein will be obtained as soon as possible within 72 hours to verify the grade of proteinuria.
- p. Urine dipstick testing for subjects with proteinuria  $\geq 2+$  should be performed on Day 15 of each cycle (or more frequently as clinically indicated) until the results have been 1+ or negative for 2 consecutive treatment cycles. Urine dipstick testing should be performed preferably at the investigational site (but may be performed locally by the primary care physician or a local laboratory if the subject does not have to come for a visit to the site). If a new event of proteinuria  $\geq 2+$  occurs, the subject must resume the Day 15 urine dipstick testing for evaluation of proteinuria until results are 1+ or negative for 2 consecutive treatment cycles. For subjects with a history of dipstick proteinuria  $\geq 2+$ , see Section 9.4.2.2 for management of proteinuria.
- q. Blood samples will be drawn for PK assessment of study drug at 0.5-4 hours and 6-10 hours postdose on C1D1; predose on C1D8; predose, 0.5-4 hours, and 6-10 hours postdose on C1D15; predose (optional) on C1D22, and predose and 2-12 hours postdose on C2D1.
- r. **Screening:** Screening tumor assessments using CT of the brain, neck, chest, abdomen and pelvis, and other areas of known or suspected disease should be performed within 28 days prior to C1D1. Detailed image acquisition guidelines will be provided by the imaging core laboratory. Scans that were performed within this window but before informed consent may be used if they were acquired consistent with the guidelines provided by the imaging core laboratory.  

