8.6 Unscheduled Visits

Data from unscheduled visits (e.g., vital signs or laboratory tests) will be excluded from the by-visit summary but will contribute to the worst value in required summary tables. Listings will include all visits, both scheduled and unscheduled.

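### From Cycle 3, Day 15 blood pressure is required only after a reading of 160/100 or above, yet the by-visit summary can show that visit unflagged beside Day 1 visits at which all subjects are due

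*SAP*

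**What the plan says.** **Schedule.** Protocol Table 7 (section 9.5.1.5) marks vital signs without condition at C1D1, C1D8, C1D15, C2D1, C2D15 and Day 1 of each later cycle; C1D22 is optional. From Cycle 3 onward the Day 15 mark carries note h: subjects with systolic BP of at least 160 or diastolic BP of at least 100 mmHg "must have their BP monitored on Day 15 or more frequently as clinically indicated", until readings are no higher than 150 systolic and 95 diastolic for two consecutive cycles. These Day 15 visits have their own visit numbers (8, 10, 12, 14 and so on).

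**Analysis.** SAP 5.6.4 says each vital sign "will be summarized/plotted by visit (only those having results for" at least 10% of subjects), as observed value and as change from Baseline. The denominator of the 10% is not given. The same section adds a hypertension shift table from Baseline to worst grade.

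**Exclusions.** SAP 8.6 addresses unscheduled data only: these "will be excluded from the by-visit summary but will contribute to the worst value in required summary tables". Nothing in the SAP treats a scheduled but conditional visit differently from any other.

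**The concern.** Whether a Day 15 BP is required from Cycle 3 depends on the subject's own earlier BP. The 10% rule counts how many subjects have results, not why they were measured. A Day 15 row or plotted point could therefore be the mean of a subset chosen for high BP, placed between Day 1 points at which all treated subjects are due. The step from Day 1 to Day 15 would then mix selection, regression to the mean and the effect of added antihypertensives with any real trend. Both arms pass through the same threshold, so the selected subsets also tend to resemble each other more than the arms do.

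This matters because hypertension was the most frequent adverse event in Study 303 and, with proteinuria, the one that most often led to dose reduction (Protocol 7.1). The trial asks whether 18 mg has a better safety profile than 24 mg, so BP over time by arm is a display that people will read.

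**Working it through.** **1. When the visit is displayed.** The documents give no figure for this issue. The only plan figure needed is the sample size, which reproduces: n per arm = 2(1.960 + 0.842)² / [0.544 × 0.456 × (ln 0.4)²] = 75.4, so 76 per arm and 152 in total. The 10% rule then needs 0.10 × 152 = 15.2, that is 16 subjects overall, or 0.10 × 76 = 7.6, that is 8 per arm. It needs fewer if the denominator is subjects still on treatment. The documents give no rate of BP at or above 160/100, so whether the threshold is reached is unknown.

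**2. Simple illustration (all inputs assumed).** Systolic mean 132, between-subject SD 13, within-subject SD 9; a subject is flagged if any of 4 earlier readings is at least 160; the next reading is averaged.

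- Flagged: 9.8%. Mean of the next reading: about 152.4 in flagged subjects, 132.0 in all.
- Gap with no treatment effect: 152.4 − 132.0 = 20.4 mmHg. For means of 128 and 136 it is about 23 and 18.
- If antihypertensives lower flagged subjects by d mmHg, the all-subject mean also falls by 0.098d, so gap = 20.4 − d + 0.098d = 20.4 − 0.902d.

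| d (mmHg) | 0 | 8 | 15 | 20 | 25 |
|---|---|---|---|---|---|
| Gap (mmHg) | +20.4 | +13.2 | +6.9 | +2.4 | −2.2 |

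- With arm means of 134 and 128 and d = 0, the flagged means are 153.2 and 151.1: a difference of 6 becomes about 2. The shares flagged are 12.4% and 5.8%, or (12.4 + 5.8)/2 = 9.1% pooled. On a pooled denominator this row would not be shown; on a per-arm denominator only the higher arm's row would be.

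**3. Simulation with note h entry and exit rules (inputs assumed).** Untreated systolic mean 128, 134 or 140 in the 24-mg arm and 4 mmHg lower in the 18-mg arm; between-subject SD 11, within-subject SD 9. The share monitored at C3D15 is 9%, 19% and 33% (24 mg) and 5%, 12% and 23% (18 mg). Results at Cycle 3, for the three means in that order:

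| Antihypertensive effect (mmHg) | Day 15 minus Day 1, 24 mg | Arm difference, Day 1 | Arm difference, Day 15 subset |
|---|---|---|---|
| 0 | +14.7, +12.2, +9.6 | 4.0, 4.0, 4.0 | 2.1, 2.3, 2.2 |
| 8 | +6.3, +4.4, +2.2 | 3.7, 3.2, 2.9 | 2.0, 2.0, 1.6 |
| 15 | +0.6, −1.1, −2.0 | 3.4, 3.0, 2.3 | 2.2, 1.9, 1.5 |
| 25 | −8.1, −8.7, −8.0 | 3.1, 2.4, 1.5 | 2.4, 2.1, 2.0 |

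Both models agree that the Day 15 mean is displaced from the all-subject level, that the sign depends on treatment effect, and that the arm contrast usually shrinks. It can exceed the Day 1 contrast when treatment is strong (2.0 against 1.5 in the last cell).

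**The case against.** A reader might infer three stronger things that the documents do not support.

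- **That the visit exists only for hypertensive subjects.** Note h is a requirement, not a bar on others. A carton holds 16 doses, and the investigator may "dispense up to 2 cartons simultaneously to a subject if it is appropriate for the subject to not return to clinic for 28 days", so others may return at two weeks. Dipstick testing for proteinuria of 2+ or more "should be performed on Day 15 of each cycle (or more frequently as clinically indicated"), although it may be done locally. Monitored subjects also stay in until two controlled cycles have passed, so many Day 15 values will be below 160/100.
- **That the plot must show a false rise.** Protocol 9.4.2.1 directs treatment at confirmed readings of 160/100 or above: "Continue study drug and institute antihypertensive therapy for subjects not already receiving this". An upward step therefore needs the 10% rule to be met and BP control to be incomplete. The simple illustration also flags on a single reading, whereas the protocol averages repeat readings and asks for a confirmatory assessment.
- **That dose differences are hidden.** Day 1 of every cycle is due for all subjects. The worst-grade shift table, the Grade 3 or higher events by preferred term, and the clinically significant event summaries for hypertension (SAP 5.6.2 and Appendix 13.1) do not use these by-visit means.

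It can also be said that SAP 5.6 reports n with descriptive statistics, so a small denominator should be visible in tables, and that the table shells, held in a separate document, may already deal with this. The first helps tables but not necessarily plots, and a smaller n does not tell the reader that the subset was selected on BP. The second cannot be checked. What stands is that direction, size and even display are uncertain; the selection itself is not answered.

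**Conclusion.** The point holds as a minor one. Cycle 3 and later Day 15 BP depends on the outcome, is scheduled, and passes the SAP's display rule unflagged once 10% of subjects have results. If shown, its means and changes from Baseline are not comparable with the adjacent Day 1 visits. The distortion may go either way: roughly +20 mmHg with no antihypertensive effect, and near zero or negative at 20 to 25 mmHg in the simple model. The model with exit rules gives +10 to +15 mmHg with no effect and about −8 to −9 at 25 mmHg. The arm contrast at these points tends to be attenuated, from 4.0 to between 2.1 and 2.3 mmHg with no treatment effect.

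These sizes rest on assumed means, SDs and treatment effects. The documents supply none of them, nor the rate of qualifying readings or the 10% denominator. The effect is confined to a descriptive safety display; no endpoint, test or sample size figure changes.

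**What to change.** In SAP 5.6.4 and 8.6, state that Day 15 vital signs from Cycle 3 onward are triggered monitoring. Either leave them out of by-visit means, changes from Baseline and plots, or show them in a separate, labelled row or panel. Keep them in the worst-grade shift table and the listings. State the denominator of the 10% rule (per arm or pooled, all treated or still on treatment). Apply the same treatment to any Day 15 dipstick results collected under Table 7 note p, since SAP 5.6.3 uses a similar 10% rule.

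The cost is a sentence or two in the SAP and a matching change to the table shells. Data collection and patient management are untouched. The one downside is that the monitored subset no longer appears in the main by-visit display; the separately labelled option keeps it in view.
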